#### 6.7.3 Concomitant Medications

Concomitant medications will be summarized by the WHO Drug substance name. Concomitant medications will be coded by preferred term using the World Health Organization (WHO) Drug Dictionary. The number and percentage of patients taking concomitant medications will be tabulated. Concomitant medications will be listed by patient.

#### 6.7.4 Deaths

The number of total deaths, deaths that occur within 30 days of last study treatment, and deaths that occur more than 30 days after last study treatment as well, as the relationship to disease, will be summarized. In addition, cause of death will be identified by descending MedDRA Preferred Term (unless otherwise specified) and summarized. Death information will be listed by patient.

# 6.7.5 Liver Safety Assessment

Liver safety assessment will be summarized based on the measurements of alkaline phosphatase (ALP), alanine transaminase (ALT), total bilirubin, and aspartate transaminase (AST).

In addition, subjects with the postbaseline liver function test results that are consistent with the Hy's law criteria will be summarized.

#### 7 INTERIM ANALYSIS

No formal interim analyses are planned. An ongoing real-time review of SAEs will be conducted by Seattle Genetics Pharmacovigilance.

# 8 CHANGES FROM PLANNED ANALYSES

# 8.1 Changes from the Original Protocol

Refer to Sec 8.2.

# 8.2 Changes from the Original SAP

The following changes are mainly due to the scope change from full CSR to abbreviated CSR unless otherwise mentioned.

- iRECIST releated endpoints are not anlyzed.
- Vital signs analyses are not presented.
- All Treated Subjects analysis set is added as the primary analysis set for efficacy analysis, and Efficacy Evaluable Analysis set is removed for CSR as it's intended for during study analysis.
- ITT analysis set is removed as this is not randomized study.
- ECG anlayses are not presented.

Study SGNLVA-002 Ladiratuzumab vedotin Statistical Analysis Plan Seagen, Inc. - Confidential 01-May-2024

- Exploratory analyses for PN like time to onset and resolution/improvement are not performed.
- ECOG status by visit are not summrized.
- Palliative radiotherapy on a non-target lesion that is not progressing is not excluded from the new antitumor treatment when calculating PFS and DOR to be conservative.

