9.2.2. Duration of Response

DOR is defined as the time from start of the first documentation of objective response (CR or PR that is subsequently confirmed), to the first documentation of disease progression (per RECIST v1.1 or per investigator claim of clinical progression), or to death due to any cause, whichever comes first.

DOR data will be censored as described below:

- Patients who do not have PD and are still on study at the time of an analysis will be censored at the date of the last disease assessment documenting absence of PD.
- Patients who have started a new antitumor treatment prior to documentation of PD will be censored at the date of the last disease assessment prior to the start of a new therapy.
 Note: Palliative radiotherapy on a non-target lesion that is not progressing will not be

- considered a subsequent anticancer therapy, however, radiotherapy on any target lesion will be considered subsequent anticancer therapy.
- Patients who are removed from the study prior to documentation of PD will be censored
 at the date of the last disease assessment documenting the absence of PD.

DOR will only be calculated for patients achieving a confirmed CR or PR.

Analysis of DOR will also be performed based on iRECIST guidelines, with iDOR defined as the time from first documentation of objective response (that is subsequently confirmed) per investigator to the first documentation of objective disease progression (that is subsequently confirmed), or to death due to any cause, whichever comes first. Disease progression is considered to be confirmed without the confirmation scan if patient has clinical progression or becomes clinically unstable.

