9.2.4. Progression-Free Survival

PFS is defined as the time from start of study treatment to first documentation of objective progression of disease (PD per RECIST v1.1 or per investigator claim of clinical progression), or to death due to any cause, whichever comes first. For patients who are enrolled but fail to receive study treatment, the enrollment date will be used as the starting point in the calculation of PFS.

The same censoring rules outlined in Section 9.2.2 for DOR will be applied to PFS. Patients lacking an evaluation of tumor response after their first dose will have their event time censored at Day 1.

Analysis of PFS will also be performed based on iRECIST guidelines, with iPFS defined as the time from start of study treatment to the first documentation of objective disease progression (that is subsequently confirmed). The date of progression is the first date at which progression criteria are met (i.e., the date of unconfirmed progressive disease [iUPD]), provided that confirmed progressive disease (iCPD) is established at the next assessment. Disease progression is considered to be confirmed without the confirmation scan if patient has clinical progression or becomes clinically unstable.

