#### 6.6.1.2 Duration of Response (DOR)

Duration of response (DOR) according to RECIST Version 1.1 is defined as the time from first documentation of objective response (that is subsequently confirmed) per investigator to the first documentation of disease progression, or to death due to any cause, whichever comes first. Disease progression includes radiologic evidence of tumor progression and clinical progression per investigator.

Duration of response will only be calculated for the subgroup of patients achieving a confirmed CR or PR. Duration of response will be analyzed using Kaplan-Meier methodology and Kaplan-Meier plots will be provided by expansion cohorts and overall. The Study SGNLVA-002

Statistical Analysis Plan

O1-May-2024
Ladiratuzumab vedotin

Seagen, Inc. - Confidential

Page 17 of 32

median duration of response and its two-sided 95% CI using the complementary log-log transformation method (Collett 1994) will be calculated for each expansion cohort and overall.

DOR data will be censored as described below:

- Patients who do not have PD and are still on study at the time of an analysis will be censored at the date of the last disease assessment documenting absence of PD;
- Patients who have started a new antitumor treatment (with the exception of palliative radiotherapy on a non-target lesion that is not progressing) prior to documentation of PD will be censored at the date of the last disease assessment prior to start of new therapy;
- Patients who are removed from the study prior to documentation of PD will be censored at the date of the last disease assessment documenting absence of PD.
- Patients who have deaths or PD per RECIST v1.1 occurring after two or more missed visits will be censored at the last disease assessment;

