# 6.6.1.4 Progression-Free Survival (PFS)

Progression-free survival (PFS) is defined as the time from start of study treatment to first documentation of disease progression (PD) based upon the disease assessment per RECIST Version 1.1 or clinical progression, or to death due to any cause, whichever comes first. For patients who are enrolled but fail to receive study treatment, the enrollment date will be used as the starting point in the calculation in PFS. Specifically,

PFS = Date of first documented PD or death - Date of first study treatment +1

The same censoring rules outlined for DOR will be applied to PFS. Patients lacking an evaluation of tumor response at baseline and/or after their first dose will have their event time censored at Day 1.

PFS will be analyzed using the Kaplan-Meier method and Kaplan-Meier plots will be provided. The median PFS and its two-sided 95% confidence intervals (CI) will be calculated using the complementary log-log transformation method (Collett 1994) by expansion cohorts and overall.

Page 18

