#### Note:

Only timepoint responses prior to new anti-cancer therapy are considered.

To classify response throughout the study, if start day of new anti-cancer therapy exists, then set B= start day of new anti-cancer therapy, otherwise B=999999.

Set A=35 days (protocol-specified minimal days for assessment of SD, the earliest day in the

Set A=35 days (protocol-specified minimal days for assessment of SD, the earliest day in the window of first scheduled assessment.).

Days A and B define the time windows for the records to be included in the best overall response assessment.

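### The SAP gives two opposite rules for palliative radiotherapy in PFS and DOR, and does not declare its missed-visit censoring rule as a change from the protocol

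*SAP*

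**What the plan says.** **Radiotherapy.** Protocol 9.2.2 censors DOR at the last assessment before new antitumor treatment and adds a note: "Palliative radiotherapy on a non-target lesion that is not progressing will not be" counted as subsequent anticancer therapy. SAP 6.6.1.2 has the same censoring rule and the same carve-out: "with the exception of palliative radiotherapy on a non-target lesion that is not progressing". SAP 8.2, which lists changes from the original SAP, says of this same radiotherapy that it "is not excluded from the new antitumor treatment when calculating PFS and DOR to be conservative".

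**Missed visits.** SAP 6.6.1.2 ends its list of DOR censoring rules with: "Patients who have deaths or PD per RECIST v1.1 occurring after two or more missed visits will be censored at the last disease assessment". Protocol 9.2.2 lists three censoring rules, and this is not among them. SAP 8.1, headed as changes from the protocol, only refers the reader to 8.2, which does not mention the rule.

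**Link to PFS.** SAP 6.6.1.4: "The same censoring rules outlined for DOR will be applied to PFS". Protocol 9.2.4: "The same censoring rules outlined in Section 9.2.2 for DOR will be applied to PFS". Whatever holds for DOR therefore holds for PFS in each document.

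**The concern.** A patient who receives palliative radiotherapy to a stable non-target lesion stays at risk under SAP 6.6.1.2, and any later progression or death counts. Under SAP 8.2 the same patient is censored at the last assessment before radiotherapy and later events are dropped. Two programmers, each following a part of the SAP, would produce different PFS and DOR. The case can arise, because Protocol 5.5.2 permits such radiotherapy on treatment with medical monitor approval.

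The missed-visit rule turns some events that the protocol counts, including deaths from any cause, into censored observations. A reader who checks the section meant for departures from the protocol would not learn of it. The rule also leaves open what a missed visit is: a clinic visit or a scheduled scan, and whether the two must be consecutive.

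PFS and DOR are secondary endpoints estimated without a control arm, so the censoring rules feed directly into the reported curves and medians. The SAP plans no sensitivity analysis for either rule.

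**Working it through.** The plan states no expected PFS or DOR, number of events or power for these endpoints, so there is no figure to reproduce. The check is a comparison of texts, followed by a test of the direction of each rule.

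**1. Texts side by side**

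| Situation | Protocol 9.2.2 / 9.2.4 | SAP 6.6.1.2 / 6.6.1.4 | SAP 8.2 |
|---|---|---|---|
| Palliative radiotherapy, non-progressing non-target lesion | Not censored | Not censored | Censored |
| Death or RECIST PD after two or more missed visits | Event | Censored | Not mentioned |

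Protocol 9.3.1.3 agrees with the second row: it censors patients who have no event.

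**2. Direction by hand.** The Kaplan-Meier estimate is S(t) = product of (1 - d/n) over event times. Take ten patients with events at months 1 to 10. Then S(5.5) = 0.50, S(6.5) = 0.40 and the median is 5. After month 3, S = 9/10 × 8/9 × 7/8 = 0.70. If one further patient is censored at month 3, six remain at risk.

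- Radiotherapy after the month-3 scan, progression would have come at month 4: S(6.5) = 0.70 × 5/6 × 4/5 = 0.467. The curve rises from 0.40.
- Same patient, progression would have come at month 10: S(6.5) = 0.70 × 5/6 × 4/5 × 3/4 = 0.35. The curve falls from 0.40.
- Missed-visit rule, death at month 6 moved back to censoring at month 3: S(5.5) = 0.70 × 5/6 × 4/5 = 0.467, down from 0.50. S(6.5) is also 0.467, up from 0.40. The median stays at 5.

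**3. Direction by simulation.** Each scenario had 400,000 patients and exponential PFS with a median of 5.5 months. That median sets the scale only; it is a background figure in Protocol 3.2.3.4. Scans follow the plan: every 6 weeks for 12 months, then every 12 weeks. All else is assumed, because the documents give no frequencies or prognosis:

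- 5% to 20% of patients are scheduled for radiotherapy, or to stop scans, at an exponential time with mean 4 months.
- The progression hazard after radiotherapy is 0.5 to 4 times baseline.
- The death hazard after stopping scans is 0.5 to 2 times baseline.

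Progression is detected on scan dates, so the median moves in steps; curve heights are compared instead.

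Change in PFS when radiotherapy is censored rather than exempted, in percentage points at 6 / 12 months:

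| Share | Hazard ×0.5 | ×1 | ×2 | ×4 |
|---|---|---|---|---|
| 5% | -0.4 / -0.8 | 0 / 0 | +0.7 / +0.7 | +1.2 / +1.0 |
| 10% | -0.8 / -1.5 | 0 / 0 | +1.3 / +1.4 | +2.4 / +2.1 |
| 20% | -1.8 / -3.0 | 0 / 0 | +2.5 / +2.9 | +5.0 / +4.2 |

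Change in PFS when the missed-visit rule is applied, in percentage points at 6 / 12 months:

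| Share | Death hazard ×0.5 | ×1 | ×2 |
|---|---|---|---|
| 5% | -0.8 / -1.0 | -0.5 / -0.3 | -0.1 / +0.3 |
| 10% | -1.6 / -1.9 | -1.0 / -0.5 | -0.1 / +0.5 |
| 20% | -3.3 / -3.9 | -2.0 / -1.1 | -0.4 / +1.0 |

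The simulation covers PFS. DOR uses the same rules but was not simulated.

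**The case against.** **Section 8.2 is only a change log.** If it described superseded text, a mismatch with the body would not be an error. But it states what the current SAP does. Its other entries agree with the body: the ITT and efficacy-evaluable sets are absent from Section 4, and vital signs and ECG analyses from 6.7. The radiotherapy entry is the one that the body contradicts.

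**The SAP may differ from the protocol.** Protocol 9.3 requires an amendment only where site conduct changes, and the missed-visit rule is stated openly in the SAP body. This stands. The fault is the missing declaration and reason in 8.1, not a prohibited change. The original SAP is not available, so the rule can be called new only relative to the protocol.

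**A reader might infer that both rules inflate PFS and DOR.** The documents do not support this. Protocol 5.5.2 describes palliative radiotherapy for stable symptomatic metastases and not to treat progression, and no document says these patients fare worse. A simulation that censors patients at the scan just before their own event would show an upward shift, but only because it builds one in. When later prognosis is allowed to vary, the shift goes either way.

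**A reader might also infer an effect on the primary ORR**, since Appendix E says: "Only timepoint responses prior to new anti-cancer therapy are considered". SAP 8.2 limits its change to PFS and DOR, and nothing extends it to best response.

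**Nor is there a PFS benchmark to be biased against.** The 5.5 months in Protocol 3.2.3.4 is background for chemotherapy in the Part D population. No document makes it a comparator, and SAP 5.7 plans no formal testing.

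**Conclusion.** Two points hold on the text alone. First, the SAP cannot be followed as written for palliative radiotherapy to a non-progressing non-target lesion: 6.6.1.2 and 8.2 give opposite instructions, and both PFS and DOR are affected. Second, censoring deaths and RECIST progression after two or more missed visits departs from Protocol 9.2.2 and 9.2.4 and is not declared in SAP 8.1 or 8.2.

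The conservative label in 8.2 is unsupported. Under the assumed ranges, censoring at radiotherapy shifts PFS by -1.8 to +5.0 points at 6 months and -3.0 to +4.2 at 12 months. The missed-visit rule shifts it by -3.3 to -0.1 and by -3.9 to +1.0. These ranges rest on assumed frequencies and hazards. They show that the sign is undetermined and do not predict what this trial will report. An upward bias is no better established than a conservative one.

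The point should be settled before the analysis is programmed. It concerns descriptive secondary endpoints only.

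**What to change.** 1. State one radiotherapy rule in SAP 6.6.1.2, 6.6.1.4 and 8.2. Use the protocol rule (exempt) as primary and keep censoring at radiotherapy as a sensitivity analysis. Drop the conservative label.
2. List the missed-visit rule in SAP 8.1 as a change from the protocol, with a reason. Define it as two or more consecutive missed scheduled disease assessments.
3. Report PFS and DOR alongside under the protocol's own censoring rules, with radiotherapy exempt and no missed-visit censoring. The protocol's censoring for other new therapy and for removal from study before progression stays in place.
4. Give the number of patients censored by each rule, so that readers can see whether the choice matters.

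The cost is a few lines of SAP text and one extra PFS and DOR run. The radiotherapy sensitivity analysis needs only a change of censoring flag in the same program. Site conduct does not change, so under Protocol 9.3 no protocol amendment is needed.

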# Appendix A Imputation of Partially Unknown Adverse Event Dates

For a pre-existing condition and adverse event (AE) with a partial start or end date, if it can be determined that the event occurred prior to the date of first dose of study treatment, the partial date will not be imputed; Otherwise, the partial date will be imputed using the rules described below. For ease of reading, both pre-existing conditions and AEs will be referred to as AE for the remainder of this document. AE start dates should be imputed before imputation of AE condition end date in all cases.

# Incomplete AE Start Date:

#### AE day only is missing

If the month/year is the same as the month/year of first dose of any study treatment and the onset period and/or onset time indicate that the start of the AE was post-dose:

AE start date will be imputed as the first dose date of any study treatment

If the month/year is after the month/year of first dose of any study treatment:

AE start date will be imputed as the first day of the month

#### AE day and month are missing, or month only is missing

If the year is the same as the year of first dose of any study treatment and the onset period and/or onset time indicate that the start of the AE was post-dose:

AE start date will be imputed as the first dose date of any study treatment

If the year is after the year of first dose of any study treatment:

AE start date will be imputed as January 1st

#### AE day, month and year are missing, or year only is missing

AE start date will be imputed as the first dose date of any study treatment

If AE condition end date\* is not missing, and the imputed start date is after the end date, the start date will be set to the AE condition end date.

#### Incomplete AE End Date:

If AE outcome is "not recovered/resolved", "unknown", or blank: AE condition end date will not be imputed.

If AE outcome is "recovering/resolving", "recovered/resolved", "recovered/resolved with sequelae", or "fatal" apply the following:

#### AE day only is missing

AE condition end date will be imputed as the minimum of (death date, data extraction date, last day of the end date month/year, EOS date)

### AE day and month are missing, or month only is missing

If the year is equal to the year of the last dose date:

Study SGNLVA-002 Ladiratuzumab vedotin Statistical Analysis Plan Seagen, Inc. - Confidential 01-May-2024

Page 24 of 32

\* only use condition end date if known and the full end date is available.

AE condition end date will be imputed as the minimum of (last dose date + 30, death date, data extraction date, December 31st of the end date year, EOS date)

If the year is not equal to the year of the last dose date:

AE condition end date will be imputed as the minimum of (death date, data extraction date, December 31st of the end date year, EOS date)

# AE day, month and year are missing, or year only is missing

AE condition end date will not be imputed

Within a single record, if the imputed stop date is before the start date, then the imputed stop date will be equal to the start date.

# Example

# AE Number 4: Condition/Event NAUSEA First dose date 02APR2012

# Prior to imputation

Log line	Start date	Condition end date	Severity	Outcome	Onset
1	UNUNK2011	25APR2012	1	not recovered/resolved	pre-ICF
2	25APR2012	UNAPR2012	2	recovering/resolving	post 1st dose
3	UNAPR2012	04MAY2012	1	recovered/resolved	post 1st dose
Post imp	utation				
Log Line	Start date	Condition end date	Severity	Outcome	Onset
1	UNUNK2011	25APR2012	1	not recovered/resolved	pre-ICF
2	25APR2012	30APR2012	2	recovering/resolving	post 1st dose
3	02APR2012	04MAY2012	1	recovered/resolved	post 1st dose

# Appendix B Imputation of Partial Missing Prior Therapy Dates

When calculating time since most recent prior therapy, please following the following algorithm.

The most recent prior therapy date is defined as the latest among all the prior therapies including therapy start and end date. And if prior therapies date are partially missing, please following the following imputation rule. Prior therapy dates will be imputed if both month and year are present and only day is missing.

- For prior therapy start date, impute the first day of the month.
- For prior therapy end date, impute the last day of the month or 1 day before the first dose of study drug, whichever is earlier.

# Appendix C Definition of the Term "Treatment-Emergent" with Respect to AE Classification

The algorithm below should be used to determine whether an adverse event (AE) is classified as a treatment-emergent adverse event (TEAE). A TEAE is defined as any AE which worsens in severity during the safety reporting period or is newly occurring at any time, where newly occurring means that the AE was not present at baseline. For ease of reading, both pre-existing conditions and AEs will be referred to as AEs for the remainder of this document. AE dates should be imputed in accordance with the algorithm detailed in Appendix A prior to determination of TEAE classification. Details of the TEAE classification are as follows:

- For each patient, determine the first dose date, which is the earliest date the patient receives any amount of study drug.
- Baseline AEs: classify an AE record as baseline AE if it satisfies both criteria a and b below:

AE onset satisfies either of i, ii or iii below:

- Onset date is prior to the first dose date
- ii. Onset date is the same as the first dose date, and Onset Period is "started after consent but before the first dose of any study treatment" or Onset Time Relative to Study Treatment is "started before first infusion or before infusion on any dosing day"
- iii. Onset Period is "started before the signing of consent" or "started after consent but before the first dose of any study treatment"

AE end date satisfies either of i or ii below:

- End date is the same as or after the first dose date
- End date is missing with outcome equal to

recovering/resolving, or

not recovered/not resolved, or

unknown or missing

- Post-baseline AEs: classify an AE record as post-baseline AE if it meets either of criteria a, b or c below:
  - a Onset date is after the first dose date
  - b Onset date is the same as the first dose date, and Onset Period is "started after the first dose of any study treatment" or Onset Time Relative to Study Treatment is not "started before first infusion or before infusion on any dosing day"
  - c Onset Period is "started after the first dose of any study treatment"
- TEAE flag will be derived as follows:
  - For all AE records that have an end date prior to the first dose date, assign TEAE flag to 'N'
  - For all baseline AEs, assign TEAE flag to 'N'
  - c. For post-baseline AEs:
    - If the post-baseline AE is a continuing event of a baseline AE (i.e., events with
      the same AE identifier, where AE identifier is the number before the colon in
      SDTM AE.AESPID), then compare the post-baseline AE to the most recent
      baseline AE with the same AE identifier (to be referred to as "baseline AE"
      below). Assign TEAE flag to "Y" for the applicable post-baseline AE records, if a

Study SGNLVA-002 Ladiratuzumab vedotin Statistical Analysis Plan Seagen, Inc. - Confidential 01-May-2024 Page 27 of 32 post-baseline AE record meets any of the following worsening criteria based on relatedness, seriousness or CTCAE grade:

- If the post-baseline AE is related to treatment, or
- If the post-baseline AE meets the criteria for an SAE and the most recent baseline AE was not an SAE, or
- If the post-baseline AE has a higher CTCAE grade

All subsequent episodes of the same AE should have TEAE flag = 'Y'.

- Otherwise, assign TEAE flag to 'N'
- If the post-baseline AE is not a continuing event of a baseline AE, then assign TEAE flag to 'Y

NOTE: For summaries which include only treatment emergent AEs, include all AEs which have at least one record classified as aTEAE as well as those AEs for which TEAE status could not be determined (e.g., the value of the TEAE variable may be missing if the event cannot be identified as baseline or post-baseline – missing information on the AE CRF should be queried). Only exclude those AEs which were determined to not be treatment emergent for all records.

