7.5.1.3. Reporting Periods for Adverse Events and Serious Adverse Events

The safety reporting period for AEs is from study Day 1 (predose) through the EOT visit or 30 days after the last study treatment, whichever is later. The reporting period for SAEs is from study Day 1 (predose) through the EOT visit or 90 days after the last study treatment, whichever is later. Events will be recorded at each examination on the Adverse Event CRFs/worksheets. However, all study protocol-related AEs are to be recorded from the time of informed consent. All SAEs that occur after the safety reporting period and are considered study treatment-related in the opinion of the investigator should also be reported to the sponsor. The investigator will make every attempt to follow all patients with non-serious AEs for outcome.

The reporting timeframe for AEs meeting any serious criteria is described in Section 7.5.1.4.

SAEs will be followed until significant changes return to baseline, the event stabilizes (recovering/resolving) or is no longer considered clinically significant by the investigator, or the patient dies or withdraws consent. All non-serious AEs will be followed through the safety reporting period. Certain non-serious AEs of interest may be followed until resolution, return to baseline, or study closure, whichever comes first. In particular these include AEs of peripheral neuropathy in all patients.

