9.3.9.2. Adverse Events

An overview of AEs will provide a tabulation of the incidence of all AEs, treatment-emergent AEs, treatment-related AEs, Grade 3 and higher AEs, SAEs, treatment-related SAEs, deaths, and AEs leading to study treatment discontinuation. AEs will be defined as treatment emergent if they are newly occurring or worsen following study treatment.

AEs will be listed and summarized by Medical Dictionary for Regulatory Activities (MedDRA), preferred term, severity, and relationship to study drug. In the event of multiple occurrences of the same AE with the same preferred term in 1 patient, the AE will be counted once as the occurrence. The incidence of AEs will be tabulated by preferred term and treatment group. AEs leading to premature discontinuation of study drug will be summarized and listed in the same manner.

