#### 6.7.1 Adverse Events

Adverse events will be summarized by MedDRA Preferred Term in descending frequency of occurrence unless otherwise specified. For incidence reporting, if a patient reports more than one AE that was coded to the same system organ class or preferred term, the patient will be counted only once for that specific system organ class or preferred term.

A treatment-emergent AE(TEAE) is defined as a newly occurring or worsening AE after the first dose of study drug, through EOT visit or 30 days after last dose date whichever is later or through EOT visit or 90 days after last dose date for SAE. See Appendix C for details

Study SGNLVA-002 Ladiratuzumab vedotin Statistical Analysis Plan Seagen, Inc. - Confidential 01-May-2024 Page 19 of 32 regarding treatment-emergent classification. An overall summary of AEs will be provided. Summaries of AEs will be provided for the following, by preferred term, if not specified otherwise:

- All treatment-emergent AEs
- Treatment-emergent AEs related to SGN-LIV1A
- Treatment-emergent AEs related to both SGN-LIV1A and Pembro
- Treatment-emergent Serious Adverse Events (SAEs)
- Treatment-emergent SAEs related to SGN-LIV1A
- Treatment-emergent SAEs related to both SGN-LIV1A and Pembro
- Treatment-emergent AEs leading to dose delay of SGN-LIV1A
- Treatment-emergent AEs leading to dose reduction of SGN-LIV1A
- Treatment-emergent AEs leading to treatment discontinuation
- Treatment-emergent AEs leading to death
- Infusion-related reactions by preferred term
- DLTs
- Treatment-emergent AEs by system organ class, preferred term and maximum severity.
- Grade 3–5 treatment-emergent AEs
- Treatment-emergent AEs by system organ class and preferred term

All adverse events, adverse events leading to treatment discontinuation, and adverse events leading to death will be listed.

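### SAP 6.7.1 and SAP Appendix C define a treatment-emergent adverse event differently, on the end of the window and on what counts as worsening, and the Appendix C algorithm can only give the higher count

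*SAP*

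**What the plan says.** **SAP 6.7.1 (Adverse Events)** defines a TEAE as a new or worsening event after first dose, and closes the window "through EOT visit or 30 days after last dose date whichever is later or through EOT visit or 90 days after last dose date", the second limit being for SAEs. It then refers to Appendix C for the detail of the classification.

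**SAP Appendix C** presents its algorithm as the one to be used. Its opening sentence says a TEAE is an AE that "worsens in severity during the safety reporting period or is newly occurring at any time". The steps then work as follows:

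- A baseline record is always flagged N.
- For a new event the rule is "If the post-baseline AE is not a continuing event of a baseline AE, then assign TEAE flag to 'Y", with no date condition.
- A post-baseline record that continues a baseline event is flagged Y if it meets any of the "worsening criteria based on relatedness, seriousness or CTCAE grade". The first of these reads "If the post-baseline AE is related to treatment, or"; the others are new seriousness and a higher grade.
- Later episodes of a flagged event are also Y, and one flagged record brings the whole event into the TEAE summaries.

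**Protocol 9.3.9.2** says "AEs will be defined as treatment emergent if they are newly occurring or worsen following study treatment". It gives no end of window.

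**Protocol 7.5.1.3** sets the collection periods: AEs to the later of EOT or 30 days after last treatment, SAEs to the later of EOT or 90 days. Beyond that, "All SAEs that occur after the safety reporting period and are considered study treatment-related" by the investigator should still be reported.

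**The concern.** The type, incidence, severity, seriousness and relatedness of AEs are primary safety endpoints. Most of the AE summaries listed in SAP 6.7.1 are restricted to treatment-emergent events, so the flag decides what goes into them. Two programmers, one working from 6.7.1 and one from Appendix C, would produce different tables from the same data.

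The differences are not neutral with respect to causality. After the reporting period essentially only treatment-related SAEs are reported, so late events that enter through the open window are selected on relatedness. Among continuing records at the same grade and seriousness as baseline, those judged related count and those judged unrelated do not. The summary of TEAEs related to SGN-LIV1A is affected by construction.

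**Working it through.** The plan gives no figure to reproduce. The check applies each rule to the same test events.

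**Rules compared**

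- *Appendix C*: post-baseline and new → Y. Post-baseline and continuing → Y if related, or newly serious, or higher CTCAE grade. No end date.
- *SAP 6.7.1*: onset no later than max(EOT, last dose + 30), or max(EOT, last dose + 90) for SAEs; and new, or higher grade.
- *Protocol 9.3.9.2*: new, or higher grade, after treatment. No end date.

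**Assumptions**

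- Last dose is on day 100 and EOT is 35 days later, on day 135. The 6.7.1 limits are then max(135, 130) = day 135 for non-serious AEs and max(135, 190) = day 190 for SAEs.
- Worsening in 6.7.1 and the protocol is read as a higher grade.
- 6.7.1 does not repeat the later-of rule for SAEs; it is taken from protocol 7.5.1.3.

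| Event | App. C | 6.7.1 | Protocol |
|---|---|---|---|
| Baseline record, no new record | N | N | N |
| Continuing, same grade, unrelated | N | N | N |
| Continuing, same grade, related | **Y** | N | N |
| Continuing, Grade 2 to Grade 1, related | **Y** | N | N |
| Continuing, same grade, newly serious, unrelated | **Y** | N | N |
| Continuing, higher grade, unrelated | Y | Y | Y |
| New SAE, last dose + 60 (day 160) | Y | Y | Y |
| New related SAE, last dose + 150 (day 250) | **Y** | N | Y |
| New non-serious AE, last dose + 60 (day 160) | **Y** | N | Y |

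The last row is only a logical difference: with EOT on day 135, protocol 7.5.1.3 does not collect that event.

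**All continuing-record profiles inside the window.** Four baseline grades × four post-baseline grades × serious at baseline (yes/no) × serious after baseline (yes/no) × related (yes/no) = 4 × 4 × 2 × 2 × 2 = 128.

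- Grade not higher than baseline: 10 of the 16 grade pairs. Under 6.7.1 all of these are N.
- Within each such pair there are 8 combinations of seriousness and relatedness. Appendix C gives Y for the 4 related ones and for 1 more that is unrelated but newly serious: 5 of 8.
- Discordant profiles: 10 × 5 = 50 of 128. In every one Appendix C gives Y and 6.7.1 gives N; the reverse never occurs.

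The figure of 50 in 128 counts logical possibilities. It is not an expected rate.

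**The case against.** Several arguments limit the point.

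- **The protocol on the window.** A reader might infer that the open window contradicts the protocol. It does not: the definition in protocol 9.3.9.2 has no end date either, and the 30- and 90-day limits in 7.5.1.3 govern collection. On the window the conflict is within the SAP. The protocol is contradicted only on worsening.
- **Unchanged baseline events.** A reader might infer that a stable Grade 1 neuropathy, which the eligibility criteria allow, becomes a TEAE once it is marked related. It does not. Baseline records are always N; relatedness is tested only on a separate post-baseline record with the same identifier. Protocol 7.5.1.1 ties recording to a change in severity, frequency or character. What remains is a new record at the same or a lower grade. SAP 6.7.1.1 also does not say that the special-importance table is restricted to TEAEs, so an effect there is not established.
- **Collection closes most of the gap.** Non-serious AEs are not collected after the window, and protocol 6.6 requires no follow-up after the safety follow-up period. Late entries would be mainly reports of related SAEs. This stands, and makes the worsening rule the likelier source of extra TEAEs.
- **The sections can be read together.** One could apply the 6.7.1 window and use Appendix C only for the remaining detail. That is a reasonable intention, but the Appendix C text on new events says the opposite.
- **The inclusive rule may be deliberate.** Appendix C lists its criteria openly, and a sponsor may want same-grade changes attributed to the drug to be visible. That is a fair choice for a safety summary, but the opening definition would have to say so. Relatedness and new seriousness fall equally outside worsening in severity, since protocol 7.5.1.1 assesses severity and seriousness independently; removing one while keeping the other needs a stated reason.

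**Conclusion.** The point holds as an inconsistency between two stated rules. SAP 6.7.1 and Appendix C differ on the end of the window. Appendix C's criteria for continuing events also do not match its own opening definition, 6.7.1 or protocol 9.3.9.2. The direction is settled, given that worsening means a higher grade: following Appendix C can add TEAEs and cannot remove any.

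The size is unknown. It depends on how many late related SAEs are reported and how many continuing baseline events acquire a related or newly serious record without a higher grade; the documents give neither number. The 2.5 points per patient in Part D (1/40) is only the weight of one case. A reader might infer that the TEAE counts are inflated; the documents support only that they can be. The study is single-arm with no formal hypothesis testing, so no test result depends on the flag. This is a low-cost correction, not a threat to the study's conclusions.

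**What to change.** 1. Add the 6.7.1 limits to the post-baseline step of Appendix C: onset no later than the later of EOT or 30 days after last dose, and for SAEs EOT or 90 days, stating whether the later applies (as in protocol 7.5.1.3). Remove the open-ended wording for new events from the opening sentence.
2. List treatment-related SAEs with onset after the window separately, so that none is lost.
3. Use one definition of worsening in 6.7.1, the Appendix C opening and the flag step: either a higher CTCAE grade only, or a definition that openly includes new seriousness. In both cases relatedness by itself should not count as worsening. Related continuing records without a higher grade can go in a separate listing.

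The cost is SAP wording and a small change to the flag derivation. No data collection changes. TEAE counts may fall slightly.
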